8.3.3. Month 24 (± 7 Days) and/or End of Treatment Visit

The following procedures and assessments will be performed at Month 24 (for subjects who complete the Treatment Period) or as soon as possible after permanently discontinuing IP (for subjects who discontinue IP early):

- Collect reasons for discontinuing IP, if applicable.
- Administer patient-reported outcome assessments.
- Review gout flares that occurred since the last study visit.
- Take vital signs.
- Measure weight.
- Assess AEs.
- Record concomitant medications.
- Assess compliance with IP (lesinurad/placebo).
- Assess compliance with XO1.

- Measure target tophi.
- Collect blood sample for hematology.
- Collect blood sample for the following serum chemistry analyses:
 - Analytes 1.
 - Analytes 2.
 - Analytes 3.
 - Pregnancy test for females of childbearing potential.
- Collect blood sample for plasma biomarkers.
- Collect urine sample for the following analyses:
 - Urinalysis.
 - Protein-creatinine ratio.
 - Urine biomarkers.
- Dispense XOI.

8.4. Follow-Up Period

All subjects who complete the Treatment Period will return to the site for an End of Study Visit 1 month later ([Section 8.4.2](#)).

Subjects who permanently discontinue IP early should return to the site for an End of Treatment visit ([Section 8.3.3](#)) as soon as possible after discontinuing IP, then a Post-End of Treatment Visit ([Section 8.4.1](#)) 1 month after the End of Treatment Visit. They should remain on study and follow the protocol schedule (with the exception of dispensing and taking IP) and have an End of Study Visit ([Section 8.4.2](#)) at the conclusion of their study period. Alternatively, if the subject does not agree to this option, a modified follow-up including, eg, regular telephone contacts or a contact at Month 24, should be arranged, if agreed to by the subject and in compliance with local data privacy laws/practices. Subjects who do not wish to continue on study after discontinuing IP should complete an End of Study Visit 1 month after treatment discontinuation ([Section 8.4.1](#)), which should be performed in place of the Post-End of Treatment Visit.

8.4.1. Post-End of Treatment Visit for Subjects Who Discontinue Investigational Product But Remain on Study (~30 Days Post-Discontinuation)

Subjects who permanently discontinue IP but remain on study should complete a Post-End of Treatment Visit approximately 28 days after the End of Treatment Visit. The following procedures and assessments will be performed:

- Administer patient-reported outcome assessments.
- Review gout flares that occurred since the last study visit.
- Take vital signs.
- Assess AEs.

- Record concomitant medications.
- Measure target tophi.
- Collect blood sample for hematology.
- Collect blood sample for the following serum chemistry analyses:
 - Analytes 1.
 - Analytes 2.
 - Analytes 3.
- Collect urine sample for the following analyses:
 - Urinalysis.
 - Protein-creatinine ratio.
- Assess compliance with XOI, if applicable.
- Dispense XOI, if applicable.

8.4.2. End of Study Visit

All subjects should complete an End of Study Visit. This visit should occur approximately 28 days after completing the Treatment Period or after permanent treatment discontinuation if the subject is no longer continuing in the study. Subjects should return all study supplies to the site. The following procedures and assessments will be performed:

- Collect reasons for early study withdrawal if applicable.
- Administer patient-reported outcome assessments.
- Review gout flares that occurred since the last study visit.
- Take vital signs.
- Assess AEs.
- Record concomitant medications.
- Measure target tophi.
- Collect blood sample for hematology.
- Collect blood sample for the following serum chemistry analyses:
 - Analytes 1.
 - Analytes 2.
 - Analytes 3.
- Collect blood sample for plasma biomarkers.
- Collect urine sample for the following analyses:
 - Urinalysis.

- Protein-creatinine ratio.
- Urine biomarkers.
- Assess compliance with XOI, if applicable.

9. PLANNED STATISTICAL METHODS

This section describes the statistical considerations and data analyses to address the objectives of the study. Further details will be provided in the Statistical Analysis Plan (SAP).

9.1. General Considerations

All subjects will be randomized to either lesinurad 200 mg or matching placebo in combination with an XOI in a 1:1 ratio and stratified by the following stratification factors:

- Screening eCrCl: the average eCrCl of Screening Visit 1 and Screening Visit 2 (30.0 to <45.0 mL/min or 45.0 to <60.0 mL/min).
- Baseline measurable target tophus status: present or absent.
- Type of XOI: allopurinol or febuxostat.

This study will enroll approximately 50% of subjects with eCrCl 30.0 to <45.0 mL/min and approximately 50% with eCrCl 45.0 to <60.0 mL/min. There is no planned sample size requirement on the number of subjects enrolled by type of XOI or Baseline tophus status. However, a stratification variable (eg, Baseline measurable target tophus status [present/absent]) may be dropped from the stratified analysis (eg, mixed model repeated measures [MMRM] or Cochran Mantel Haenszel [CMH]) if the number of subjects in any stratum is very low (eg, <10% of total subjects). The decision to drop a stratification variable will be made prior to database lock and will be documented in the SAP.

All safety and efficacy data will be listed and summarized by treatment group.

Baseline is defined as the last observed measurement prior to the first dose of IP, unless otherwise specified.

Descriptive statistics will consist of the number of subjects (n), mean, standard deviation (SD), median, minimum, and maximum for continuous variables, and counts and percentages for categorical variables.

Unless otherwise specified, all confidence intervals (CIs) will be calculated at the 95% level and all hypothesis tests will be performed at the 0.05 level. All analyses including summaries and listings will be performed using SAS[®] software version 9.1 or higher.

9.2. Determination of Sample Size

Approximately 600 subjects will be randomized 1:1 to either the lesinurad (LESU) + XOI or placebo (PBO) + XOI group in this study.

For safety endpoint analyses, this sample size provides sufficient precision around the estimated between-treatment difference for the absolute and percent changes in eCrCl from Baseline to Month 24 based on the normal distribution CI with 95% two-sided confidence level. For the difference in absolute change from Baseline to Month 24, the estimated precision is ± 1.6 mL/min assuming a common SD for the change from Baseline in each treatment group of 10 mL/min estimated from the lesinurad Phase 3 development program. For the difference in percent change from Baseline to Month 24, the estimated precision is $\pm 3.2\%$ assuming a common SD for the

percent change from Baseline in each treatment group of 20% estimated from the lesinurad Phase 3 development program.

For the key efficacy endpoint analyses, this sample size will provide >90% power for the overall population and >80% power within each Screening eCrCl stratum to detect a treatment difference for the proportion of subjects achieving sUA <6.0 mg/dL at Month 6 of 15% (20% in the PBO + XOI group versus 35% in the LESU + XOI group, as estimated from the lesinurad Phase 3 development program), using a binomial distribution at an alpha of 0.05 (two-sided). Based on the assumptions above, this sample size provides sufficient precision such that the minimum statistically significant difference in response rate is approximately 10% in the overall population, and approximately 11% in the Screening eCrCl 30.0 to <45.0 mL/min stratum, at the two-sided 5% level.

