4. STUDY POPULATION SELECTION

4.1. Study Population

Approximately 600 subjects will be enrolled (300 per treatment group).

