9.4.3. Efficacy Analyses

Efficacy data will be summarized and analyzed in the ITT population.

The key sUA efficacy endpoint (proportion of subjects with sUA <6.0 mg/dL at Month 6) will be summarized descriptively by treatment group and a comparison of the response rates will be presented using the CMH test statistic, stratified by type of XOI, Baseline measurable target tophus status (present/absent), and Screening eCrCl (30.0 to <45.0 mL/min or 45.0 to <60.0 mL/min), as appropriate as stated in [Section 9.1](#). Results will be expressed as proportions, corresponding adjusted 95% CI of the difference between response rates, and p-values. Subjects who are missing their Month 6 sUA results will be analyzed as non-responders.

The LESU + XOI group will be deemed superior compared with the PBO + XOI group if there is sufficient statistical evidence to reject the following null hypothesis:

H₀: $p_1 = p_2$ ie, no evidence that the proportion of subjects achieving an sUA response by Month 6 in the LESU + XOI group is different from the PBO + XOI group.

and in favor of the alternative hypothesis:

H₁: $p_1 \neq p_2$ ie, the proportion of subjects achieving an sUA response by Month 6 in the LESU + XOI group is different from the PBO + XOI group.

The key efficacy endpoint will be tested in the overall study population as well as the subset of subjects whose Screening eCrCl is 30.0 to <45.0 mL/min. To account for multiplicity, a hierarchical testing procedure will be performed to preserve an overall alpha at 0.05 level. First, the null hypothesis for the key efficacy endpoint will be tested in the overall population at an alpha level of 0.05. If the null hypothesis is not rejected, the testing will be stopped. Otherwise, the endpoint will then be tested in the subset of subjects whose screening eCrCl is 30.0 to <45.0 mL/min at an alpha level of 0.05.

Sensitivity analyses (eg, observed cases or other imputation approaches) will be explored to assess the impact of missing data (details provided in the SAP).

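### Section 9.2 overstates the minimum significant difference in the overall population: its own assumptions give about 7% (7–8% depending on test and rate), not about 10%

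*Combined protocol and SAP*

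**What the plan says.** Protocol Section 9.2 sets the size of the trial: "Approximately 600 subjects will be randomized 1:1 to either the lesinurad (LESU) + XOI or placebo (PBO) + XOI group in this study". For the key efficacy endpoint, the proportion with sUA below 6.0 mg/dL at Month 6, it assumes "20% in the PBO + XOI group versus 35% in the LESU + XOI group, as estimated from the lesinurad Phase 3 development program", and it describes the power calculation as "using a binomial distribution at an alpha of 0.05 (two-sided"). It claims power above 90% overall and above 80% in each Screening eCrCl stratum. It then adds, expressly on those assumptions: "minimum statistically significant difference in response rate is approximately 10% in the overall population, and approximately 11% in the Screening eCrCl"; the second figure is for the stratum below 45.0 mL/min, and both are for a two-sided 5% test.

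Section 9.1 fixes the stratum size: "This study will enroll approximately 50% of subjects with eCrCl 30.0 to <45.0 mL/min and approximately 50% with eCrCl 45.0 to <60.0 mL/min". Section 9.4.3 fixes the denominator and the decision rule. On missing data it says "Subjects who are missing their Month 6 sUA results will be analyzed as non-responders". Significance is decided by a stratified CMH test at 0.05 in the overall population, followed, if that succeeds, by the same test at 0.05 in the lower eCrCl stratum.

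**The concern.** The two thresholds are too close together. For fixed response rates, the smallest significant difference shrinks roughly with the square root of the sample size. The lower eCrCl stratum is about half the trial, so its threshold should be about √2 = 1.41 times the overall one. The printed ratio is 11/10 = 1.1, so both figures cannot rest on the same assumptions.

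The sentence is the plan's only statement of how precise the key efficacy comparison will be. If the overall figure is wrong, a reader would take an observed difference of 8 points as falling short of significance when it would not. The reader would also conclude that the whole trial is barely more precise than a subgroup of half its size, and the plan tests those two populations in sequence.

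**Working it through.** **Inputs.** 600 subjects randomized 1:1, so 300 per arm (Sections 4.1 and 9.2). About half are in the lower eCrCl stratum, so about 150 per arm there (Section 9.1). Rates of 20% and 35%, two-sided 5% (Section 9.2). Full alpha of 0.05 for the overall test, and missing Month 6 values counted as non-response (Section 9.4.3).

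**Step 1: the other figures in Section 9.2 reproduce.**
- Power for 20% versus 35% (pooled-variance normal approximation): 98.6% with 300 per arm and 83.2% with 150 per arm, matching the stated >90% and >80%.
- eCrCl precision: 1.96 × 10 × √(2/300) = 1.60 mL/min and 1.96 × 20 × √(2/300) = 3.20%, as stated.

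**Step 2: normal approximation to the threshold.**
- Unpooled, 300 per arm: 1.96 × √[(0.20×0.80 + 0.35×0.65)/300] = 1.96 × √(0.3875/300) = 7.04%.
- Unpooled, 150 per arm: 1.96 × √(0.3875/150) = 9.96%.
- Pooled at 27.5%: 1.96 × √(2 × 0.275 × 0.725/n) = 7.15% for n = 300 and 10.11% for n = 150.

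**Step 3: search over counts for the smallest difference with p < 0.05.**

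| Rate held fixed | Test | Overall (300 per arm) | Stratum (150 per arm) |
|---|---|---|---|
| Control 20% | chi-square | 7.0% (60 vs 81) | 10.0% (30 vs 45) |
| Control 20% | continuity-corrected or Fisher | 7.3% (60 vs 82) | 10.7% (30 vs 46) |
| Treatment 35% | chi-square | 7.7% (105 vs 82) | 10.7% (52 vs 36) |
| Treatment 35% | continuity-corrected or Fisher | 8.0% (105 vs 81) | 11.3% (52 vs 35) |

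(35% of 150 is 52.5; 52 was used.) The stated 11% lies within the stratum range. The stated 10% lies outside the overall range.

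**Step 4: other response rates.** With control rates from 20% to 50% in 5-point steps and 300 per arm, the largest threshold is 8.7% (continuity-corrected, control 45%). None reaches 10%.

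**Step 5: consistency of the two printed figures.** 11%/√2 = 7.8% overall. Conversely, 10% × √2 = 14.1% in the stratum.

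**Step 6: what a 10-point result would show.** 60/300 versus 90/300 gives p = 0.0047 (chi-square), 0.0063 (continuity-corrected) and 0.0061 (Fisher). Even 8 points, 60/300 versus 84/300, gives p = 0.022 (chi-square) and 0.028 (Fisher).

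**Step 7: possible explanations for 10%.**
- *Attrition.* Section 9.2 makes no allowance, and the non-responder rule keeps the denominator near 300. If 30% were nonetheless lost (an assumption), leaving 210 per arm, the unpooled value would be 8.4%. Reaching 10% on that formula needs 1.96² × 0.3875/0.10² ≈ 149 per arm, half the trial.
- *Difference detectable with 80% power.* This is 9.9% with 300 per arm, but 14.3% with 150 per arm, so it cannot produce 11% for the stratum. The text also speaks of statistical significance, not detectability.
- *Split alpha.* Section 9.4.3 gives the overall test the full 0.05.
- *Stratum sample size used by mistake.* The unpooled value for 150 per arm is 10.0%. That is a possible source, but the documents do not show it.

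**The case against.** The strongest objection concerns consequence. Nothing in the plan uses the 10% figure. Significance rests on the CMH p-value, and the figure does not feed the sample size, the power statements, the testing order or any success criterion. The synopsis gives the sample-size argument without this sentence. The error is conservative: the trial can reach significance at a smaller difference than the text says. All of that stands, and it is why the point is minor.

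A second objection is that a bare 7% would claim more than the arithmetic supports. The threshold is 7.0% by chi-square anchored at 20% control and 8.0% by Fisher anchored at 35% treatment, and scaling down from the accepted 11% gives 7.8%. Chi-square at 20% control also pairs 7.0% with 10.0% in the stratum, not 11%. This stands too, so the correction should carry the 7–8% range and use one test and one anchor for both figures.

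A third objection is that Section 9.2 does not show the method behind the sentence, and that the planned analysis is a CMH test with up to three stratification factors, which the check does not model. That limits the second digit. It does not plausibly close a gap that would need the sample to be halved. Likewise, requiring one dose for the ITT population may bring the denominator slightly below 300, but not to about 150.

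**Conclusion.** The concern holds. On Section 9.2's own assumptions, the minimum significant difference in the overall population is 7.0–8.0%. The stated 10% is therefore too high by about 2 to 3 points at the stated rates, and by at least 1.3 points (10 − 8.7) at any control rate tried from 20% to 50%. The stratum figure of about 11% is sound.

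This rests on 300 and 150 subjects per arm in the denominators, a two-sided 5% test, and unstratified two-sample tests standing in for the CMH. Severity is minor: the figure misdescribes the precision of the key efficacy comparison but changes no decision the plan makes.

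**What to change.** In Section 9.2, replace the overall figure with approximately 7% (7–8% depending on test and rate) and leave the stratum figure at approximately 11% (10–11% depending on test). Name the test and the anchoring rate, the same for both populations. For example, Fisher's exact test anchored at 20% control gives 7.3% and 10.7%; anchored at 35% treatment, it gives 8.0% and 11.3%.

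The cost is one sentence. Sample size, power and the hierarchical CMH test stay as they are, and no new data are needed.

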9.3. Analysis Populations

The **Intent-to-Treat (ITT) Population** will be defined as all randomized subjects who received at least 1 dose of IP (lesinurad or placebo). This will be the primary population for efficacy analyses and subjects will be analyzed based on the randomized treatment assigned.

The **Safety Population** will be defined as all randomized subjects who received at least 1 dose of IP (lesinurad or placebo). Subjects will be analyzed based on the randomized treatment assigned. Any major deviations from the randomized treatment assignment will be listed and considered when interpreting the safety data.

The **Per-Protocol Population** will be defined as all subjects in the ITT population without major protocol deviations, defined prior to unblinding of the study. Select analyses (to be specified in the SAP), will be repeated on the PP population.

9.4. Analysis Methods

9.4.1. Disposition, Demographics, and Baseline Characteristics

Subject disposition, demographics, gout diagnosis, and Baseline disease and treatment characteristics will be summarized for the ITT Population.

Compliance with IP (lesinurad or placebo) will be summarized and will include the number of subjects estimated to be <80% compliant, 80% to 120% compliant, and >120% compliant. The total dose and average daily dose will also be summarized.

9.4.2. Safety Analyses

Safety data will be analyzed descriptively using the Safety Population.

The main estimands to address the safety objective are the absolute and percent changes from baseline to Month 24 in eCrCl, assessed in the Safety population, with treatment difference estimated using MMRM and missing data imputed separately for each treatment group assuming missing at random (MAR).

9.4.2.1. Change From Baseline in Estimated Creatinine Clearance

Absolute and percent changes from Baseline to Month 24 in eCrCl will be assessed using a MMRM analysis that includes terms for treatment (LESU + XOI and PBO + XOI), visit, treatment by visit interaction, stratification factors (type of XOI [allopurinol or febuxostat], Baseline measurable target tophi status [present/absent], and Screening eCrCl [30.0 to <45.0 mL/min or 45.0 to <60.0 mL/min], as appropriate as stated in [Section 9.1](#)), and Baseline eCrCl as covariate. The model will assume an unstructured covariance matrix. If convergence issues are encountered, alternative covariance structure will be explored (details will be provided in the SAP). Least-square (LS) mean by treatment and LS mean difference between LESU + XOI and PBO + XOI alone will be estimated from the MMRM analysis, along with the 95% CI of LS mean difference.

All subjects should be followed for safety events even if they discontinue IP (lesinurad or placebo), as permitted. Prior to performing MMRM analysis, renal function data that are collected after subjects discontinue IP will be set to missing. All missing data will be imputed using multiple imputation methodology assuming MAR and separate imputation models for the LESU + XOI and PBO + XOI groups. Sensitivity analysis will include all available data (including data after subjects discontinue IP) and impute only for missing data assuming MAR. Additional sensitivity analysis will be performed using multiple imputation assuming missing not at random, depending on the nature of missing data and early treatment discontinuations (eg, subjects discontinuing early due to worsening renal function).

In addition to using the Cockcroft-Gault equation for eCrCl, renal function will also be evaluated using estimated glomerular filtration rate (eGFR) equations (eg, the Modification of Diet in Renal Disease [MDRD]), and may be explored using similar methods as above.

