3. INVESTIGATIONAL PLAN

3.1. Overall Study Design and Plan

This study will be conducted in up to approximately 300 sites in North America and Europe. Subjects with gout, moderate renal impairment, and who are not at target sUA of <6.0 mg/dL on XOI alone will be enrolled. The study will include an approximate 1-month Screening Period, a 24-month Double-Blind Treatment Period, and a 1-month post-treatment Follow-Up Period.

To be eligible for the study, subjects must be on a stable, medically appropriate dose of XOI as their sole ULT indicated for the treatment of gout for at least 4 weeks prior to Screening and throughout the Screening Period. Investigators should have followed the treatment guidelines to determine the medically appropriate dose of XOI. During the Screening Period, subjects will complete 2 Screening Visits: Screening Visit 1 (approximately 1 month before the Baseline Visit) and Screening Visit 2 (3 weeks after Screening Visit 1 [± 3 days]). To be eligible for the study, estimated creatinine clearance (eCrCl; calculated by the Cockcroft-Gault formula using ideal body weight) must be 25.0 to ≤ 65.0 mL/min at each Screening Visit and the average eCrCl of both Screening Visits must be 30.0 to <60.0 mL/min, which is the Screening eCrCl. Additionally, subjects must have an sUA level ≥ 6.0 mg/dL (387 $\mu\text{mol/L}$) at both Screening Visits.

Subjects who qualify for the study will be randomized at the Baseline Visit (4 to 7 days after Screening Visit 2) in a double-blind fashion to 1 of 2 treatment groups in a 1:1 ratio:

- LESU + XOI: lesinurad 200 mg qd and XOI.
- PBO + XOI: placebo qd and XOI.

Randomization will be stratified by the Screening eCrCl subgroup (30.0 to <45.0 mL/min or 45.0 to <60.0 mL/min), Baseline measurable target tophus status (present/absent), and type of XOI (allopurinol or febuxostat). This study will enroll approximately 50% of subjects with eCrCl 30.0 to <45.0 mL/min and approximately 50% with eCrCl 45.0 to <60.0 mL/min. When the maximum number of subjects in one of the eCrCl subgroups has been reached, subsequent enrollment will be limited to subjects in the other eCrCl subgroup. There are no limitations on the number of subjects enrolled by type of XOI or Baseline tophus status.

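### The main eCrCl model uses one Baseline value and a two-level Screening stratum; adding the continuous Screening mean would narrow the confidence interval slightly at almost no cost

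*Combined protocol and SAP*

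**What the plan says.** Section 9.4.2 makes the absolute and percent changes in eCrCl to Month 24 the principal safety estimands. Section 9.4.2.1 models them by MMRM with treatment, visit, their interaction, the three stratification factors and "Baseline eCrCl as covariate". Under Section 9.1, "Baseline is defined as the last observed measurement prior to the first dose of IP", unless another rule is given, so Baseline is one value.

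Screening eCrCl is a different quantity. Section 3.1 requires that "the average eCrCl of both Screening Visits must be 30.0 to <60.0 mL/min, which is the Screening eCrCl". It enters the MMRM only as the randomization stratum: 30.0 to <45.0 or 45.0 to <60.0 mL/min.

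Creatinine belongs to the Analytes 1 panel run by the central laboratory (Section 6.9.1, Table 1). The panel is drawn at Screening Visit 1, Screening Visit 2 and the Baseline Visit (Sections 8.1.1 to 8.1.3). Baseline falls 4 to 7 days after Screening Visit 2. Appendix A, footnote g, has eCrCl calculated for each Screening Visit and for their average. The protocol does not place the continuous Screening values in the main model. It lists no predictors for the imputation models, and Section 9 leaves further detail to the SAP, of which the document contains no text.

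**The concern.** Each subject has three eCrCl measurements within about a month before dosing, and the model uses one of them at full resolution. The other two are averaged and cut at 45 mL/min, so a subject with a Screening mean of 31 is coded the same as one with 44.

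A single eCrCl equals the subject's underlying level plus assay and day-to-day error. Once Baseline is a covariate, analysing absolute change or the raw Month 24 value gives the same treatment contrast, so Baseline error does not enter the residual directly. What remains is uncertainty about the subject's underlying level, and two more measurements reduce it.

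The matter is precision. Section 9.2 justifies the safety sample size by the width of the confidence interval alone, so width is the plan's own criterion.

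**Working it through.** **Reproducing the plan's figure.** Section 9.2 states: "Approximately 600 subjects will be randomized 1:1 to either the lesinurad (LESU) + XOI or placebo (PBO) + XOI group", hence 300 per arm. Precision is "based on the normal distribution CI with 95% two-sided confidence level", and "the estimated precision is ± 1.6 mL/min assuming a common SD for the change from Baseline in each treatment group of 10 mL/min".

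Half-width = 1.96 × SD × √(2/300) = 0.16003 × SD

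- SD 10 mL/min gives 1.600 mL/min (stated: ±1.6).
- SD 20% gives 3.201% (stated: ±3.2%).

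Both reproduce. They are unadjusted and assume 300 evaluable subjects per arm.

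**Where the gain comes from.** Let s be the SD of the error in one eCrCl value, τ² the between-subject variance of the underlying level and D the variance of true change. Then SD of change 10 means D + 2s² = 100. The residual variance at Month 24 is D + s² + v, where v is what remains unknown about the underlying level:

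- one pre-dose value: v = s²τ²/(τ² + s²)
- three pre-dose values: v = s²τ²/(3τ² + s²)

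For illustration take s = 4, with the underlying level uniform on 30 to 60, so τ² = 30²/12 = 75 and D = 100 − 32 = 68.

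- One value: v = 1200/91 = 13.19. Residual variance 97.19, SD 9.86, half-width 1.578.
- Three values: v = 1200/241 = 4.98. Residual variance 88.98, SD 9.43, half-width 1.510.

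This ignores the eligibility window and the Screening stratum. A simulation that includes both, with the same inputs, gives 1.575 with Baseline alone, 1.544 with Baseline plus stratum (as planned) and 1.509 with the continuous Screening mean added. The stratum thus recovers (1.575 − 1.544)/(1.575 − 1.509) = 0.031/0.066, or about half, of the available gain. The rest is what the plan gives up.

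**Range over the unknown error.** The documents do not give s, so it is varied. Settings: underlying eCrCl uniform on 20 to 70, independent errors, protocol screening window applied, SD of change about 10, one million candidates per row.

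| s (mL/min) | Half-width, planned | With Screening mean | Narrower by | Equivalent n per arm |
|---|---|---|---|---|
| 2 | 1.596 | 1.580 | 1.0% | 306 |
| 3 | 1.579 | 1.549 | 1.9% | 312 |
| 4 | 1.553 | 1.514 | 2.5% | 316 |
| 5 | 1.506 | 1.459 | 3.1% | 320 |
| 6 | 1.450 | 1.395 | 3.8% | 324 |

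With the underlying level uniform on 30 to 60, the gain is 1.0% to 2.9%.

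**Same question with error as a CV.** A separate simulation with SD of change 10 gave these residual SDs, multiplied here by 0.16003:

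- CV 6%: 9.89 → 9.75, half-width 1.583 → 1.560 (1.4% narrower)
- CV 8%: 9.78 → 9.57, half-width 1.565 → 1.531 (2.1%)
- CV 10%: 9.52 → 9.29, half-width 1.523 → 1.487 (2.4%)

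In sample-size terms, (9.89/9.75)² = 1.029 and (9.52/9.29)² = 1.050, so about 3% to 5%, or 18 to 30 of 600. With the screening window and stratum included, the same CVs gave 1.6%, 2.3% and 2.9%. Allowing a correlation of 0.5 between the Screening Visit 2 and Baseline errors gave 1.3% to 2.4%.

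**Percent change.** The relative gain is 1.0% to 3.0% over s = 2 to 6. Only the relative figure is usable. The simulated unadjusted half-widths of 3.80 to 4.30 imply SDs of about 24% to 27% (half-width ÷ 0.16003), above the plan's 20%.

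**The case against.** The planned model is conventional: continuous Baseline, stratification factors as randomized, unstructured covariance. Nothing in it is biased or contradictory. The unadjusted ±1.6 mL/min is already called sufficient, safety is analysed descriptively with no margin or test on eCrCl, and no stated conclusion turns on 0.04 mL/min. The within-subject error is an outside assumption. The calculation looks at Month 24 alone with complete data, whereas the plan fits all visits after multiple imputation with post-discontinuation values set to missing. The imputation predictors may yet include Screening eCrCl.

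Most of this stands as a limit on importance. The gain is small, its size is assumed, and the imputation point is one for the SAP to settle, since no omission can be shown. None of it reverses the direction: the CI narrowed in every setting tried, with the stratum already in the comparison model. Correlation between Screening and Baseline eCrCl is no obstacle either. Both are measured before randomization and only the treatment contrast is of interest. For the same reason, regression to the mean caused by the eligibility window does not bias that contrast.

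**Conclusion.** The point holds as a minor efficiency improvement. The plan collects two further pre-dose eCrCl values and uses them only through a cut at 45 mL/min. Using their mean as a continuous covariate narrows the CI for the absolute change by 1.4% to 2.4% at an assumed CV of 6% to 10%, and by about 1% to 4% over error SDs of 2 to 6 mL/min.

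These figures assume SD of change 10 mL/min, 300 evaluable subjects per arm, and a Month 24 level that tracks the pre-dose level apart from true change and error. If the SD of change were 8, the gain would be 2.8% to 5.4% for error SDs of 3 to 5 mL/min. The effect of missing data and imputation was not quantified.

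**What to change.** State in the SAP, before unblinding, that the MMRM for absolute and percent change in eCrCl includes Screening eCrCl (mean of Screening Visits 1 and 2) as a continuous covariate alongside Baseline eCrCl and the stratification factors. Name the same variable as a predictor in both arms' imputation models; it may help most for subjects with few on-treatment values.

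Leave the Baseline definition unchanged for computing change and percent change and for every clinical threshold tied to it, so the estimand and subject management are unaffected. The cost is one sentence in the SAP and one degree of freedom, with no additional blood draw or data collection.
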